## 6.1.5 Fidelity of the intervention (Symptoms Clinic)

All participants will be asked that their Symptoms Clinic consultation be audio-recorded as part of the consent process. These will be archived for quality assurance purposes and a

sample (50% during the first 6 weeks, 25% thereafter) will be transcribed, with selected sections such as dialogue relating to explanation highlighted for review by members of the research team.

Fidelity will be assessed from consultation transcripts or recordings against standards developed in the preliminary studies in three ways: (a) proportion of consultation time spent on different components of the intervention [19], (b) number and type of explanations for symptoms proposed [15], (c) nature and outcome of discussion about explanations [16].

# 6.1.6 Recruitment, training and supervision of practitioners to deliver the intervention

ER-GPs will be recruited to deliver the Symptoms Clinic in each centre. They will undergo six days of training during the set-up phase of the study and deliver one clinical session per week during the delivery phase.

Local investigators will advertise for and recruit GPs to be trained in and deliver the intervention. Shortlisted candidates will be interviewed and 3 or 4 GPs per location identified for initial training. Following the initial training two will be appointed as ER-GPs for the study.

Once appointed, the ER-GPs will receive further training as follows: (1) two days of training at the University of Sheffield; (2) supervised practice in the ER-GP's own practice in which the GP will see patients following the symptoms clinic model, record the consultations and review them with the local investigator; (3) at least two further half-day training sessions at their local centre. The content of training is defined in the GP manual and follows that used in the second preliminary study.

Towards the end of the training period, ER-GPs will record a set of three consultations in their own practice for review, quality assessment and constructive feedback by a panel comprising the CI and two other investigators. Patient consent will be obtained for the recording of training consultations, and supervision / review from the CI and local investigators.

During the study, ER-GPs will receive clinical supervision. This will take place monthly with a local investigator within their contracted sessions. The supervision will include review of consultation content and encourage reflective learning and consolidation of skills.

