## 6.1.7 Separation of Symptom Clinic intervention from routine care

There is the potential for participants allocated to the usual care arm of the trial to be exposed to the intervention and the ER-GP. We will minimise the risk of participants receiving routine care from the ER-GPs (of whom there will only be two in each of the three study centres) as follows: (1) where a ER-GP conducts all his or her routine clinical work in one small-medium sized practice (<12,000 patients) we will not recruit participants from that practice; (2) where a ER-GP conducts routine clinical work either in a large practice ( $\geq$ 12,000 patients) or in a portfolio fashion across several practices, we may enrol patients from those practices but will ensure that these participants are not seen in the Symptoms Clinic by a ER-GP who might see them in routine care.

To minimise the risk of ER-GPs using the consultation techniques outside of the trial, all ER-GPs will undertake not to conduct extended consultations using the SCI model in their usual practices (after the training period)."

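### The separation undertaking leaves out 3 to 6 GPs who had the initial training, and no criterion excludes patients already seen under the clinic model in training; the dilution is probably small and cheap to prevent

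*Protocol*

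**What the plan says.** Protocol section 6.1.6 describes recruitment and training in stages. Candidates are shortlisted and interviewed, with "3 or 4 GPs per location identified for initial training. Following the initial training two will be appointed as ER-GPs for the study". Three training components follow appointment, one of them being "supervised practice in the ER-GP's own practice in which the GP will see patients following the symptoms clinic model". Towards the end of training, "ER-GPs will record a set of three consultations in their own practice for review".

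Section 6.1.7 recognises that usual-care participants might be exposed to the intervention, and sets out safeguards. All of them are written for ER-GPs, "of whom there will only be two in each of the three study centres":

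- Practice rule 1: if an ER-GP does all routine work in one practice of fewer than 12,000 patients, nobody is recruited from that practice.
- Practice rule 2: if an ER-GP works in a larger practice or across several, patients from those practices may be enrolled, but they must not be seen in the Symptoms Clinic by an ER-GP who might also see them routinely.
- Undertaking: "all ER-GPs will undertake not to conduct extended consultations using the SCI model in their usual practices (after the training period".

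Among the exclusion criteria in section 4, the nearest is number 5, which covers treatment under way at screening. Number 3 leaves it to the GP to judge whether an invitation is inappropriate. Neither refers to an earlier consultation under the clinic model.

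**The concern.** The safeguards cover fewer people than the training exposes, by two routes.

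**Trained but unappointed GPs.** The GPs who are not appointed have had the initial training, and they were recruited locally, in the areas where identification practices are sought. Section 6.1.7 places no undertaking on them, so nothing in the protocol asks them not to use extended consultations of this kind with patients who are in the usual-care arm.

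**Patients seen in training.** The undertaking starts only after the training period, because training requires ER-GPs to use the model on their own patients. Under practice rule 2 some of those practices can recruit. A patient who has already had such a consultation could then be invited, pass every criterion and be randomised.

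Exposure of controls reduces the between-arm difference. Exposure before randomisation does so in both arms: a previously treated patient allocated to the clinic may have less left to gain, and one allocated to usual care has already had part of the intervention. Either way PHQ-15 and healthcare use move towards no difference, and section 6.1.7 does not provide for recording the exposure.

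**Working it through.** **Inputs from the protocol.** GPs trained, 3 or 4 per location, and appointed, 2 per location (6.1.6); centres, 3 (6.1.7); practices, about 51 (section 4); target difference 2 points and SD 5 (8.1.1); 188 per arm, 90% power, alpha 0.05, 25% loss and 6% inflation (8.1.2). Sidedness is not stated; two-sided is assumed.

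**The plan's own figure.** n per arm = 2(1.96 + 1.2816)² × 5²/2² = 131.3, so 132 by the normal approximation. 132/0.75 × 1.06 = 186.6, so 187. The t-test version gives 133, and 133/0.75 × 1.06 = 188.0. The stated 188 is reproduced.

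**GPs outside the undertaking.** 3 × 3 − 6 = 3 and 3 × 4 − 6 = 6.

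**Size of the first route.** The protocol does not say where these GPs work or whom they would see, so this is an illustration. Assume each works in a different participating practice and recruitment is equal across practices. Controls per practice = 188/51 = 3.69, so 3 to 6 practices hold about 11 to 22 controls, or 5.9% to 11.8% of the arm. Let c be the share of all controls who receive the full effect. Then:

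- diluted difference = 2(1 − c)
- power = Φ(diluted difference / (5√(2/n)) − 1.96)

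Analysed n is 188 × 0.75 = 141 per arm, or 133 if the 6% allowance is used up.

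| Share of controls in those practices fully exposed | Practices | c | Difference | Power, n = 141 | Power, n = 133 |
|---|---|---|---|---|---|
| none | – | 0 | 2.00 | 91.9% | 90.4% |
| a quarter | 3 | 1.5% | 1.97 | 91.1% | 89.5% |
| a quarter | 6 | 2.9% | 1.94 | 90.3% | 88.6% |
| all | 3 | 5.9% | 1.88 | 88.5% | 86.7% |
| all | 6 | 11.8% | 1.76 | 84.2% | 82.1% |

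**Size of the second route.** The number of patients seen in training is not stated. The recorded sets alone give 6 × 3 = 18 consultations, which is a floor and does not count patients. If those were 18 different patients, all were invited, and they were recruited at the roughly 8% rate expected in Appendix 1, they would give 18 × 0.08 = 1.4 participants, about 0.7 of them controls. Practice rule 1 reduces this further. More training patients would raise it in proportion.

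**The case against.** The strongest reply is that little of the intervention can leak. Unappointed GPs have the initial training only; supervised practice on patients and the later sessions come after appointment. The intervention is a manualised clinic with a consultation of about 50 minutes, two or three follow-ups and monthly supervision for those who deliver it. Nothing suggests that an unappointed GP would have the time or role to reproduce it. This largely stands, and it is why the full-effect assumption is a worst case. It does not account for the undertaking stopping at the appointed GPs. The initial training may also not be trivial: ER-GPs receive six days, and the formal sessions listed after appointment come to at least three (two days plus two half-days). If the six include the initial training, that could be up to about three days, although the protocol does not say so.

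On training patients, the reply is that practice rule 1 already removes those of any ER-GP based wholly in one practice under 12,000, that the rest would be randomised to both arms, and that benefit already gained is partly reflected in the baseline PHQ-15 for which the primary model adjusts. All of this stands. It limits the route to large or multiple practices and makes it small, but does not close it.

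A reader might infer that usual-care participants will in fact receive the clinic from these GPs, or that treated training patients contaminate the control arm specifically. The protocol supports neither. It does not place any unappointed GP in a participating practice, and randomisation would put training patients in either arm.

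**Conclusion.** The gap in wording is real: 3 to 6 GPs with initial training fall outside the undertaking, and patients exposed during training in a large or multiple-practice setting can be enrolled. The direction is towards no difference. The size cannot be derived from the protocol and is probably small: a loss of 0.03 to 0.06 points from the 2-point target if a quarter of controls in 3 to 6 practices were fully exposed, with power at 91.1% to 90.3% for 141 analysed per arm. The 0.12 to 0.24 points and 88.5% to 84.2% power in the worst case need every unappointed GP to work in a different participating practice and every control there to receive the whole effect. A reader might take those figures as the expected loss; nothing in the protocol supports that. This is a cheap improvement to the protection of the contrast, and no material threat to the primary result has been shown.

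**What to change.** Two changes of wording:

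1. In section 6.1.7, extend the undertaking not to conduct consultations using the Symptoms Clinic model in usual practice to every GP who attended any Symptoms Clinic training, whether or not appointed.
2. In section 4, and in the criteria repeated in Appendix 1, exclude patients previously seen in a consultation using the Symptoms Clinic model, including training consultations. Apply this at the stage 2 practice screen or in the research nurse's screening call. The call is the fallback where the GP who screens the list is not the one who trained.

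The cost is one amendment, 3 to 6 undertakings from GPs outside the trial team, one added screening check and a handful of excluded patients.

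Two wider steps are not recommended. Extending practice rule 2 to unappointed GPs would do nothing, because it governs only who sees participants in the clinic and they never work there. Barring their practices altogether would give up as many as 3 to 6 of about 51 practices for a probably small gain, which is a trade-off against recruitment.

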## 6.1.7 Separation of Symptom Clinic intervention from routine care

There is the potential for participants allocated to the usual care arm of the trial to be exposed to the intervention and the ER-GP. We will minimise the risk of participants receiving routine care from the ER-GPs (of whom there will only be two in each of the three study centres) as follows: (1) where a ER-GP conducts all his or her routine clinical work in one small-medium sized practice (<12,000 patients) we will not recruit participants from that practice; (2) where a ER-GP conducts routine clinical work either in a large practice ( $\geq$ 12,000 patients) or in a portfolio fashion across several practices, we may enrol patients from those practices but will ensure that these participants are not seen in the Symptoms Clinic by a ER-GP who might see them in routine care.

To minimise the risk of ER-GPs using the consultation techniques outside of the trial, all ER-GPs will undertake not to conduct extended consultations using the SCI model in their usual practices (after the training period)."

# 7. Assessments and procedures

## 7.1 Primary outcome measure

The primary outcome will be physical symptoms (PHQ-15) [20] at 52 weeks after randomisation. PHQ-15 comprises 15 physical symptoms, with each accorded 2,1 or 0 points based on how much they have bothered the patient over the last 4 weeks (bothered a lot, bothered a little, not at all). In our preliminary studies a change of 3 points between baseline and 13 weeks (from a mean baseline score of 15) was associated with at least one grade of improvement (out of seven) on the Patient Global Indicator of Change (PGIC). We therefore regard this 3 point change as clinically important to individual patients.

## 7.2 Secondary outcome measures

Secondary outcomes will include quality of life (EQ-5D-5L, SF-6D, and ICECAP [21] capabilities based measures) over 52 weeks after randomisation and healthcare use over the 52 week period (GP consultations, referrals & diagnostic tests including imaging and endoscopy). In particular, we will record referral to / involvement with other symptom management services such as for pain or fatigue. We will measure participants' overall impression of change with the PGIC. We will also collect the Ability to Participate in Social Roles and Activities (PROMIS) measure to capture social functioning. There will also be data collection time points at 13 and 26 weeks to examine short and mid-term treatment effects (see *Table 1* for details).

## 7.3 Process and related measures

To understand factors associated with participants symptoms; depression, anxiety and health related concerns will be measured using the PHQ-9 [22], the Somatic Symptoms Disorder – B criteria scale (SSD-12) [23] and the Generalised Anxiety Disorder Assessment (GAD-7). We will also measure patients' health literacy using the HLS EU-6 which was developed for the 2011 European Health Literacy survey and captures health literacy skills across a range of understanding and self-management areas.

## 7.4 Measurement of outcomes

Self-report measures will be collected by questionnaire at the enrolment interview and follow up measures by post at 13, 26 and 52 weeks. Non-responders will be followed up using contact details provided by the participant to check that the outcome measures have been received by the participant and to prompt them to return the outcome measures. We will attempt to contact on all contact details provided by the participant, this may include telephone contact, email, text message and postal letter. At all contact points details of how the participant can contact the research team will be included and an offer to complete the questionnaires over the telephone will be made. The research team will adhere to the data collection procedure document when following up non-responders.

Healthcare use data will be collected from primary care records. If primary care records cannot be accessed then the participant self-report questionnaire data will be used. Timing of outcomes are shown in *Table 1*.

Outcome Measures	Source	Time			Post randomisation	
		Screening	Recruitment*	13 weeks	26 weeks	52 weeks
Physical Symptoms (PHQ-15)	PQ	~	√	~	~	~
Health profile SF12	PQ		√	~		~
NHS primary and secondary health care use	CR					~
Self-reported healthcare use	PQ				~	~
PHQ-9 & SSD-12	PQ		√	~		~
GAD-7	PQ		√	~		
EQ-5D-5L & ICECAP	PQ		✓	~	EQ-5D-5L	~
Patient Global Impression of Change	PQ			~		~
HLS EU-6	PQ		√	1		~
PROMIS	PQ		✓	~		~

### Table 1.

To avoid the risk of bias researchers collecting and handling outcome measures will be blinded to allocation of the participant. The extraction of health resource use data from medical records will be completed after all other measures have been collected from the participant as it is possible that the outcome assessor will be unblinded through exposure to correspondence in the notes. The health resource use data collection form and record review guidance will outline the order in which data is to be collected so correspondence is the last section to be reviewed.

Figure 1: Flow chart of assessments and follow-up.

The total trial period is 42 months. Participants will be in the study for approximately 52 weeks. This will include a baseline visit, initial appointment at the Symptoms clinic and up to three follow up appointments. Follow up outcome measures will be collected at 13, 26 and 52 weeks post randomisation as described in *Figure 1.* This will be collected through postal questionnaires or the option of telephone completion.

Travel expenses will be reimbursed for participants attending the baseline appointment and all Symptoms Clinic consultations. These expenses will include the cost of taxi fares. Participants will receive a £10 high street voucher on completion of the 52 week questionnaires.

# 7.5 Participant withdrawal, discontinuation and loss to follow up

Participants may withdraw from active participation in the study on request. Individuals withdrawn from the intervention will not be replaced and will be followed up for all outcomes, unless they specifically request to be withdrawn from follow up data collection. We will ask permission to collect their healthcare resource use from their GP practice at 52 weeks; participants will have the opportunity to opt out of this on withdrawal. The reason for withdrawal from the intervention/study, if known, will be recorded on a Case Report Form (CRF). However, data up to the time of consent withdrawal will be included in the data reported for the study.

If an enrolled patient is found to have a new clinical condition causing their symptoms, the ER-GP will report this to the usual care GP and CI. A decision about further study appointments will be discussed on an individual case basis; guided by the participants' choice as to whether they wish to continue attending the appointments. If a participant is withdrawn from the intervention on this basis follow up data will still be collected and included in the intention to treat analysis.

A participant will be considered lost to follow up if they do not return the participant completed outcome measures at 52 weeks after all reminder options have been utilised, according to the outcome data follow up guidance, ie. no response to telephone contact, reminder letter or email. If a participant does not respond to earlier follow up questionnaires (at 13 and 26 weeks) we will still approach at subsequent follow up time points.

## 7.6 Site & trial closure procedures

The end of the trial is defined as completion of all follow-up data for the last participant. Sites will be closed once all CRFs have been entered on to the database and data cleaning has been completed. The Research Ethics Committee (REC) will be informed of trial closure.

# 8. Statistics

## 8.1 Sample size

## 8.1.1 Definition of effect size

In the pilot trial we observed an average 3.2 point clinically important change in the intervention group from baseline to 13 weeks, compared to a 1.4 point change in the control group. We have thus powered the trial on a between group difference of 2 points on PHQ-15 (equivalent to a clinically important 3 point change from baseline)

We have based calculations of effect size on a pooled standard deviation of 5; this is larger than that seen in our preliminary studies owing to their restricted eligibility range and more in keeping with observational studies. This results in a standardised effect size of 0.4, which is similar to that seen in two small European studies of extended GP consultations for broadly comparable patients [25, 26].

## 8.1.2 Calculation of sample size

Allowing for 25% loss to follow up, and a further pragmatic 6% inflation to allow for minor treatment centre imbalances or differences, a sample of 188 patients per arm has 90% power (alpha = 0.05) to detect this effect. Therefore 376 participants will be recruited.

## 8.2 Statistical analysis

Full details of all analyses will be provided in the Statistical Analysis Plan, which will be reviewed by the Trial Steering Committee (TSC) and the Data Monitoring and Ethics Committee (DMEC) prior to analysis.

The primary outcome will be analysed using a general linear model correcting for baseline PHQ-15. Secondary outcomes will be analysed in a similar manner within a generalised linear modelling framework using appropriate link functions for the outcomes' distributions. The primary outcome will be analysed using observed data with no imputation for missing data, but we will assess the amount and patterns of missing data and test the sensitivity of estimates of treatments effects using an appropriate imputation strategy. We will explore potential modification of the treatment effect by including treatment-by-subgroup interactions in models. All treatment effect estimates will be presented with 95% confidence intervals.

A single main analysis will be performed at the end of the trial when all follow up has been completed. Interim analyses will be performed if requested by the DMEC and Standard Operating Procedure (SOP) ST004 will be adhered to maintain the integrity of the trial.

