## Inclusion criteria:

- 1. Aged between 18 69 years (inclusive) at the time of the computer search
- 2. Current physical symptoms which meet the below criteria
  - a. clinical records suggest MUS (presence of at least one code for an MUS syndrome or at least two codes for negative investigations)
  - b. records show at least 2 referrals for specialist opinion or diagnostic investigations in the last 3 years
  - c. records show no evidence of any previous or current major illnesses likely to cause multiple symptoms
  - d. doctors in the GP practice do not believe that the majority of the patient's symptoms can be currently explained by other pathology;
  - e. the score on the self-completed PHQ-15 symptoms scale is between 10 and 20 (inclusive)

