# **5.** Randomisation and enrolment

Enrolment will take place in a location within primary care, in which the Symptoms Clinic will also be held, by CRN or practice research nurses. The research nurse or delegated member of the research team will discuss the study with the patient, complete the informed consent process and collect baseline data. It must be made completely and unambiguously clear that participation in the study is entirely voluntary and that consent to participate in the study can be withdrawn at any time without affecting their future care.

The research nurse taking consent will ensure that the participant has a copy of the PIS and will also provide the participants with a copy of the completed consent form. The original consent form will be filed in the Investigator Site File and a second copy will be kept with the participant's notes.

Randomisation will be completed after consent has been obtained and baseline data collected (details of baseline measures in section 7.4). Patients will be individually

randomised (1:1) and will be allocated to the Symptoms Clinic plus usual care or usual care alone using a computer generated pseudo-random list, stratified by study centre with random permuted blocks of varying sizes. Randomisation will be via SCRAM, the Sheffield CTRU-hosted web-based randomisation system and will be in accordance with their Standard Operating Procedures (SOPs). The sequences will be held on a secure server and will be concealed until recruitment, data collection and analyses are complete.

The research nurse or delegated member of the research team will enter the participant demographic details, PHQ-15 score and confirmation of consent directly into the randomisation system. If internet access is not available there will be a reserve method to contact the central trial team at the University of Sheffield by telephone and provide these details for a member of the core team to enter into the randomisation system. The research nurse will then inform the participant of their allocation, and if assigned to the intervention make a first appointment to attend the Symptoms clinic. All participants (intervention and control) will be advised to continue to use healthcare services as and when they deem appropriate. Sheffield CTRU will confirm the allocation and appointment details (if applicable) in a letter to the participant.

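### The primary model adjusts for one pre-randomisation PHQ-15 score although two are collected; adding the screening score would give a small gain in precision

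*Protocol*

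**What the plan says.** The primary outcome is PHQ-15 at 52 weeks. The instrument is completed twice before allocation:

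- **Screening.** Under section 4, Stage 3, patients return a completed PHQ-15 by post and the trials unit checks it for eligibility. Inclusion criterion 2e requires that "the score on the self-completed PHQ-15 symptoms scale is between 10 and 20 (inclusive").
- **Enrolment.** Section 7.4 has self-report measures collected at the enrolment interview. The PHQ-15 row of Table 1 is ticked under both Screening and Recruitment.

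Section 8.2 states the primary model in one sentence, "The primary outcome will be analysed using a general linear model correcting for baseline PHQ-15", and leaves full details to the statistical analysis plan. It names one covariate, does not point to a column of Table 1 and does not mention the screening score.

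Section 5 places the collection of baseline data after consent and before randomisation, and refers to section 7.4 for the measures. Staff then enter the "PHQ-15 score and confirmation of consent directly into the randomisation system", without saying which of the two scores is meant.

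**The concern.** An earlier measurement of the outcome is usually among the best predictors of its later value. A single PHQ-15 score carries measurement error and short-term fluctuation. A second score taken at another time before randomisation therefore adds information about a participant's underlying level, even when the two are strongly correlated.

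The stated model uses one score. The other is already held for nearly everyone, because no one can be found eligible without it. What is at stake is the width of the confidence interval for the primary comparison. Bias, type I error and the planned sample size are not affected.

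**Working it through.** **1. The plan's own figure.** Inputs from sections 8.1.1 and 8.1.2: "We have thus powered the trial on a between group difference of 2 points on PHQ-15"; "We have based calculations of effect size on a pooled standard deviation of 5"; 25% loss; 6% inflation; 90% power; alpha 0.05, taken as two-sided.

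- Normal approximation: n = 2(1.960 + 1.282)² / 0.4² = 131.4, so 132 per arm. The t-based value is 132.3, so 133.
- Inflation: 133 × 1.06 / 0.75 = 187.97, so 188 per arm. Starting from 132 gives 186.6, so 187.

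The stated 188 reproduces. It takes no credit for any covariate, so the required sample size does not depend on this point. With 188 × 0.75 = 141 analysed per arm, unadjusted power at SD 5 is 91.9%.

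**2. Two scores against one, without range restriction.** Let ρ be the correlation of each pre-randomisation score with the 52-week score, and r the correlation between the two pre-randomisation scores. The residual variance factors are

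- one score: 1 − ρ²
- two scores: 1 − 2ρ²/(1 + r)

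At ρ = 0.5 and r = 0.7 these are 0.750 and 0.706, a ratio of 0.941. Over ρ 0.4-0.6 and r 0.6-0.8 the further cut is 2-14%. These figures are too favourable here, because the screening score is restricted to 10-20 and so carries less information.

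**3. With the restriction.** Simulation: normal scores with SD 5 before selection, rounded and limited to 0-30, keeping only those with a screening score of 10-20. The correlations and the pre-selection mean are assumptions, since the protocol gives none. Results for a pre-selection mean of 15:

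| r | ρ | Residual SD, enrolment only | Residual SD, both | Variance ratio | Power at 141 per arm, enrolment only → both |
|---|---|---|---|---|---|
| 0.70 | 0.5 | 4.268 | 4.205 | 0.971 | 97.6% → 97.9% |
| 0.80 | 0.5 | 4.302 | 4.254 | 0.978 | 97.4% → 97.7% |
| 0.70 | 0.6 | 3.907 | 3.804 | 0.948 | 99.0% → 99.3% |
| 0.80 | 0.6 | 3.958 | 3.881 | 0.962 | 98.9% → 99.1% |
| 0.80 | 0.7 | 3.506 | 3.389 | 0.934 | 99.8% → 99.9% |
| 0.85 | 0.7 | 3.533 | 3.442 | 0.949 | 99.7% → 99.8% |

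A pre-selection mean of 12 gives ratios of 0.937 to 0.979. The further cut at these central values is therefore about 2-7%. Taking r down to 0.6 with ρ at 0.7 extends the range to about 12%.

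The absolute powers are high partly because selection on screening also narrows the spread of the 52-week score, to an SD of about 4.1 to 4.6. The differences between models are what matter.

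**4. What 2-7% means.**

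- Interval width scales with the residual SD: √0.98 = 0.990 and √0.93 = 0.964, so about 1-4% narrower.
- In participants, with 2 × 141 = 282 analysed: 282/0.98 − 282 ≈ 6 and 282/0.93 − 282 ≈ 21.
- Power rises by less than 1 percentage point in every row above.

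**The case against.** The strongest reply is that nothing here is an error. Adjusting for one baseline measure of the outcome is standard and valid, the gain from a second is small and rests on assumed correlations, and covariate detail can be left to the analysis plan. Most of this stands, and it is why the severity is low. What it does not answer is that section 8.2 already states the covariate set for the primary model, and that set leaves out a score the trial holds.

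A reader might infer four stronger points. The protocol does not support them.

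- **That baseline PHQ-15 is undefined, or may mean the screening score.** Section 5 ties baseline data to the period after consent and before randomisation and refers to section 7.4, which places collection at the enrolment interview. Sections 4 and 7.4 speak of a baseline visit, and section 9.2 lists baseline beside 13, 26 and 52 weeks. The postal form is called a screening questionnaire. The enrolment score is the natural reading; only a direct pointer to the Table 1 column is lacking, and the note to that column's asterisk is not visible in the text available.
- **That the screening score is discarded.** Nothing rules it out as a further covariate, and the analysis plan, which was not available, may include it.
- **That regression to the mean distorts change from baseline.** It would matter only if the screening score served as baseline. Section 8.2 plans no within-arm change analysis, and the 3-point figure in section 7.1 comes from preliminary studies. In simulation the untreated drop from screening to enrolment is about zero at a pre-selection mean of 15.
- **That the unspecified score entered at randomisation could matter.** Allocation is stratified by centre only, so the score cannot affect it.

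**Conclusion.** The point holds as a modest improvement in efficiency. PHQ-15 is measured twice before randomisation and the stated primary model uses one score, naturally the enrolment score. Adding the screening score would lower residual variance by roughly 2-12% over the assumed correlations, and by about 2-7% at central values. The treatment estimate is unbiased with or without it, type I error is unaffected, and the 188 per arm stands.

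The size rests on assumed correlations, on normality before selection and on equal correlation of the two scores with the 52-week score. The direction depends less on these assumptions: the gain vanishes only if the screening score predicts nothing beyond the enrolment score. Low severity.

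**What to change.** In section 8.2, and in the analysis plan if it does not already do so:

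1. State that baseline PHQ-15 is the score collected at the enrolment visit, before randomisation (the Recruitment column of Table 1).
2. Add the screening PHQ-15 as a second covariate in the primary model.

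Both should be fixed before any outcome data are seen by arm. As optional tidying, section 5 could say which score is entered in the randomisation system.

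The cost is a sentence or two and one degree of freedom out of about 282 analysed participants. No new data are needed, because the trials unit already receives both scores, and the sample size does not change. The two covariates will be correlated, which makes their own coefficients harder to interpret but does not harm the treatment estimate.
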